14. ETHICS

14.1. Ethics Review

This protocol, the informed consent document, relevant supporting information, and all types of subject recruitment or advertisement information must be approved by the appropriate EC before the study is initiated. Any amendments to the protocol must also be approved, where necessary, by the EC prior to implementing changes in the study. Documentation of these approvals must be provided to Chimerix (or designee) prior to the initiation of the amendment.

The investigator's responsibilities regarding the EC are as follows:

- Obtain EC approval of the protocol, informed consent document, and any advertisements for subject recruitment prior to their use. Maintaining this documentation in the site's study file.
- Obtain EC approval for any protocol amendments and revisions to the informed consent document before implementing the changes. Maintaining this documentation in the study file.
- Provide the EC with any required information before or during the study.
- Submit progress reports to the EC, as required, during the conduct of the study; request re-review and approval of the study, as needed; provide copies of all EC re-approvals and relevant communication to Chimerix (or designee).
- Notify the EC within the required timeframe of all serious and unexpected AEs related to the study drug that are reported to you by Chimerix (or designee). The investigator is responsible for updating the EC on the progress of the study and of any changes made to the protocol at least once a year or at regular intervals as required. The investigator must also keep the EC informed of any AEs at the site, according to the EC policy.
- Notify the EC of protocol deviations according to the EC's policy. Maintaining this documentation in the site's study file.

14.2. Ethical Conduct of the Study

The study will be performed in accordance with ethical principles that have their origin in the Declaration of Helsinki and are consistent with ICH GCP and applicable regulatory requirements in the respective territory where the study is conducted.

14.3. Written Informed Consent/Assent

The investigator is responsible for obtaining written informed consent from each individual participating in this study after adequate explanation in layman's terms regarding the nature of the study, along with the purpose, methods, objectives, and any potential risks or benefits.

Written assent should be obtained from minor subjects in accordance with institution practice using an assent form that summarizes the study in age-appropriate language, as approved by the EC.

The informed consent document shall also contain the subject's authorization for the use and disclosure of his/her protected health information (PHI) in connection with the study. The authorization shall include at a minimum a clear description of the following: the duration of the authorization, the subject's right of access to the PHI (or any suspension thereof during the course of the study), type of information to be used/disclosed in the study, the names or classes of parties that may use or disclose the PHI, the purpose of the use/disclosure of PHI, the extent of the subject's right to revoke the authorization, the extent to which participation in the study is conditioned on signing the authorization, and the potential for re-disclosure of PHI.

The informed consent/assent document must be appropriately signed and dated by the subject or the subject's legally authorized representative and the person obtaining the consent (if required by the EC) prior to conducting/obtaining any study-related assessments including the discontinuation of any medications prohibited for the study.

If the informed consent/assent document(s) is amended during the study (e.g., new safety information), the investigator must follow all applicable regulatory requirements pertaining to approval of the amended informed consent/assent document(s) by the EC prior to use. All new subjects enrolling in the study should be consented with the amended, approved informed consent/assent document(s), including ongoing subjects in treatment as directed by the EC.

The investigator must maintain the original and any amended signed and dated informed consent document(s) and/or assent form(s) as applicable. A copy of the signed informed consent document(s) or assent form(s) must be given to the subject or the subject's legally authorized representative.

15. DATA HANDLING AND RECORD-KEEPING

15.1. Data Collection

All observations relating to the study will be recorded by site personnel in source documents. In addition, eCRFs will be provided for this study. An eCRF must be completed for every subject entered into the study. The eCRF must be completed according to the eCRF completion guidelines. After each subject has completed the study, the investigator must review and electronically sign the eCRFs indicating that (s)he has reviewed the completed eCRFs and pertinent clinical data for the subject and that, to the best of his/her knowledge, all data recorded in the eCRFs accurately reflects the subject's performance in the study.

15.2. Inspection of Records

Chimerix (or its designee) will be allowed to conduct site visits to the investigation facilities for the purpose of monitoring any aspect of the study. The investigator agrees to allow the monitor to inspect the drug storage area, study drug stocks, drug accountability records, subject charts and study source documents, and other records related to study conduct.

15.3. Retention of Records

Essential documents maintained in conduct of the study should be retained for one of the following time periods:

- At least 2 years after approval of the last marketing application,
OR
- At least 2 years have elapsed since the formal discontinuation of clinical development of the investigational product.

These documents should be retained for a longer period (e.g., 15 years or more), however, if required by applicable local or country-specific regulatory requirements or by an agreement with Chimerix. It is the responsibility of Chimerix to inform the investigator/institution as to when these documents no longer need to be retained. If it becomes necessary for Chimerix or any regulatory authority to review any documentation relating to the study, the investigator must permit access to such records.

15.4. Confidentiality

Subject names will remain confidential and will not be supplied to Chimerix or its designee. If the subject name appears on any other document collected (e.g., clinic discharge summary), it must be redacted before the document is transmitted to Chimerix or its designee. All study findings will be stored in electronic databases. Subjects will give explicit permission for representatives of Chimerix or its designee, regulatory authorities, and the relevant EC to inspect their medical records to verify the information collected. Subjects will be informed that all personal information made available for inspection will be handled in the strictest confidence and in accordance with Health Insurance Portability and Accountability Act (HIPAA; in USA) or national data protection/privacy laws (outside of the USA).

Individual subject medical information obtained during this study is confidential and its disclosure to third parties other than those mentioned in the preceding paragraph is prohibited. Medical information obtained during this study may be provided to the subject's personal physician or other appropriate medical personnel when required in connection with the subject's continued health and welfare and with the subject's prior knowledge and permission.

16. PUBLICATION POLICY

It is the intention of Chimerix to publish the results of this study in their entirety within a reasonable period of time following the completion of the study. Chimerix will determine when and where data will be first disclosed.

Details of this study protocol will be posted to a publically accessible register(s) to the extent required by applicable laws and regulations prior to the first subject enrolling into the study, or as regional applicable.

All information generated from this study is the proprietary property of Chimerix. Chimerix reserves the right, among other things, to:

- Modify or amend study material to ensure that no confidential or proprietary information is disclosed.
- Ensure that the reported data are factually correct.
- Utilize the information generated from or as a result of this study in any manner it deems appropriate, including but not limited to regulatory submissions, annual reports, and other scientific or business affairs of the company.
- Modify the publication or disclosure or delay it a sufficient time to allow Chimerix to seek patent protection of any invention contained therein.

Please refer to the separate agreement for this research for further specifics on publication.

APPENDIX 1. ACUTE GRAFT VERSUS HOST DISEASE NIH STAGING SCALE

The following table, adapted from the Center for International Blood & Marrow Transplant Research (CIBMTR): 2100 Post-HCT Follow-up Form, Question 169 (<https://www.cibmtr.org/manuals/fim/1/en/topic/f2100-q131-233>), should be used for staging acute GVHD.

Table 12: NIH Staging of Acute GVHD by Extent of Organ Involvement

Stage	Extent of Organ Involvement		
	Skin ^a	Liver (Total Bilirubin) ^b	Gut (Stool Output) ^c
0	No GVHD rash	< 2 mg/dL [SI: < 34 µmol/L]	< 280 mL/m ² /day or < 10 mL/kg/day
1	Rash on < 25% BSA	2 to 3 mg/dL [SI: 34 to 51 µmol/L]	280 to 555 mL/m ² /day or 10 to 19.9 mL/kg/day or persistent nausea ^d
2	Rash on 25 to 50% BSA	> 3 to 6 mg/dL [SI: > 51 to 103 µmol/L]	556 to 833 mL/m ² /day or 20 to 30 mL/kg/day
3	Rash on > 50% BSA	> 6 to 15 mg/dL [SI: > 103 to 257 µmol/L]	> 833 mL/m ² /day or > 30 mL/kg/day
4	Generalized erythroderma with bullous formation	> 15 mg/dL [SI: > 257 µmol/L]	Severe abdominal pain with or without ileus, and/or grossly blood stool

^a Use “Rule of Nines” (see [Table 13](#) below) or burn chart to determine extent of rash.

^b Range given as total bilirubin. Downgrade one stage if an additional cause of elevated bilirubin has been documented.

^c Range given as volume of diarrhea based on body surface area (BSA) or body weight in kilograms. Downgrade one stage if an additional cause of diarrhea has been documented

^d Persistent nausea with histologic evidence of GVHD of the stomach or duodenum.

Table 13: Percent Body Surfaces

Body Area	Percent	Total Percentage
Each arm	9%	18%
Each leg	18%	36%
Chest & Abdomen	18%	18%
Back	18%	18%
Head	9%	9%
Pubis	1%	1%

APPENDIX 2. BCV DOSING TABLES

Separate dosing tables are provided for subjects receiving BCV with concurrent cyclosporine (Table 14) and for subjects receiving BCV without concurrent cyclosporine (Table 15).

Please verify that you are using the correct table for each individual subject.

Both tables present the volume of BCV oral suspension (in mL) to be administered for BIW administration (second columns) and QW administration (fourth column) in the event that the BCV dose is consolidated in response to a treatment-emergent toxicity.

Look down the table for the appropriate weight range for your subject based on his or her lowest recorded body weight measurement (in kilograms) in the 30-day period prior to Day 1.

Note: A 5-mL dosing syringe is recommended for BCV doses ≤ 50 mg (i.e., ≤ 5 mL), and a 10-mL dosing syringe is recommended for BCV doses > 50 mg (i.e., > 5 mL).

Table 14 BCV Suspension Volume by Dosing Weight for Subjects Receiving Concurrent Cyclosporine

BCV BIW: 1.4 mg/kg dose		BCV QW: 2.8 mg/kg dose (Dose Consolidation)	
Dosing weight (kg) ^a	BCV Suspension Volume	Dosing weight (kg) ^a	BCV Suspension Volume
5 to 5.3	0.7 mL	5 to 5.3	1.4 mL
5.4 to 6.1	0.8 mL	5.4 to 6.1	1.6 mL
6.2 to 6.8	0.9 mL	6.2 to 6.8	1.8 mL
6.9 to 7.5	1 mL	6.9 to 7.5	2 mL
7.6 to 8.2	1.1 mL	7.6 to 8.2	2.2 mL
8.3 to 8.9	1.2 mL	8.3 to 8.9	2.4 mL
9 to 9.6	1.3 mL	9 to 9.6	2.6 mL
9.7 to 10.3	1.4 mL	9.7 to 10.3	2.8 mL
10.4 to 11.1	1.5 mL	10.4 to 11.1	3 mL
11.2 to 11.8	1.6 mL	11.2 to 11.8	3.2 mL
11.9 to 12.5	1.7 mL	11.9 to 12.5	3.4 mL
12.6 to 13.6	1.8 mL	12.6 to 13.6	3.6 mL
13.7 to 15	2 mL	13.7 to 15	4 mL
15.1 to 16.4	2.2 mL	15.1 to 16.4	4.4 mL
16.5 to 17.8	2.4 mL	16.5 to 17.8	4.8 mL
17.9 to 19.3	2.6 mL	17.9 to 19.3	5.2 mL
19.4 to 20.7	2.8 mL	19.4 to 20.7	5.6 mL
20.8 to 22.2	3 mL	20.8 to 22.2	6 mL
22.3 to 23.6	3.2 mL	22.3 to 23.6	6.4 mL
23.7 to 25	3.4 mL	23.7 to 25	6.8 mL
25.1 to 26.4	3.6 mL	25.1 to 26.4	7.2 mL
26.5 to 27.8	3.8 mL	26.5 to 27.8	7.6 mL
27.9 to 29.3	4 mL	27.9 to 29.3	8 mL
29.4 to 30.7	4.2 mL	29.4 to 30.7	8.4 mL
30.8 to 33.9	4.5 mL	30.8 to 33.9	9 mL
34 to 37.5	5 mL	34 to 37.5	10 mL
37.6 to 41.1	5.5 mL	37.6 to 41.1	11 mL
41.2 to 44.6	6 mL	41.2 to 44.6	12 mL
44.7 to 47.9	6.5 mL	44.7 to 47.9	13 mL
≥ 48	7 mL	≥ 48	14 mL

^a Dosing weight = lowest body weight (in kilograms) within 30 days prior to Day 1.
Abbreviations: BCV = brincidofovir; BIW = twice weekly; QW = once weekly

[figure not shown]
Table 15 BCV Suspension Volume by Dosing Weight for Subjects NOT Receiving Concurrent Cyclosporine

BCV BIW: 2 mg/kg dose		BCV QW: 4 mg/kg dose (Dose Consolidation)	
Dosing weight (kg) ^a	BCV Suspension Volume	Dosing weight (kg) ^a	BCV Suspension Volume
5 to 5.2	1 mL	5 to 5.2	2 mL
5.3 to 5.7	1.1 mL	5.3 to 5.7	2.2 mL
5.8 to 6.2	1.2 mL	5.8 to 6.2	2.4 mL
6.3 to 6.7	1.3 mL	6.3 to 6.7	2.6 mL
6.8 to 7.2	1.4 mL	6.8 to 7.2	2.8 mL
7.3 to 7.7	1.5 mL	7.3 to 7.7	3 mL
7.8 to 8.2	1.6 mL	7.8 to 8.2	3.2 mL
8.3 to 8.7	1.7 mL	8.3 to 8.7	3.4 mL
8.8 to 9.5	1.8 mL	8.8 to 9.5	3.6 mL
9.6 to 10.5	2 mL	9.6 to 10.5	4 mL
10.6 to 11.5	2.2 mL	10.6 to 11.5	4.4 mL
11.6 to 12.5	2.4 mL	11.6 to 12.5	4.8 mL
12.6 to 13.5	2.6 mL	12.6 to 13.5	5.2 mL
13.6 to 14.5	2.8 mL	13.6 to 14.5	5.6 mL
14.6 to 15.5	3 mL	14.6 to 15.5	6 mL
15.6 to 16.5	3.2 mL	15.6 to 16.5	6.4 mL
16.6 to 17.5	3.4 mL	16.6 to 17.5	6.8 mL
17.6 to 18.5	3.6 mL	17.6 to 18.5	7.2 mL
18.6 to 19.5	3.8 mL	18.6 to 19.5	7.6 mL
19.6 to 20.5	4 mL	19.6 to 20.5	8 mL
20.6 to 21.5	4.2 mL	20.6 to 21.5	8.4 mL
21.6 to 23.7	4.5 mL	21.6 to 23.7	9 mL
23.8 to 26.2	5 mL	23.8 to 26.2	10 mL
26.3 to 28.7	5.5 mL	26.3 to 28.7	11 mL
28.8 to 31.2	6 mL	28.8 to 31.2	12 mL
31.3 to 33.7	6.5 mL	31.3 to 33.7	13 mL
33.8 to 36.2	7 mL	33.8 to 36.2	14 mL
36.3 to 38.7	7.5 mL	36.3 to 38.7	15 mL
38.8 to 41.2	8 mL	38.8 to 41.2	16 mL
41.3 to 43.7	8.5 mL	41.3 to 43.7	17 mL
43.8 to 46.2	9 mL	43.8 to 46.2	18 mL
46.3 to 47.9	9.5 mL	46.3 to 47.9	19 mL
≥ 48	10 mL	≥ 48	20 mL

^a Dosing weight = lowest body weight (in kilograms) within 30 days prior to Day 1.

[figure not shown]
Abbreviations: BCV = brincidofovir; BIW = twice weekly; QW = once weekly

APPENDIX 3. FLOW CHART FOR BRINCIDOFOVIR DOSING ALGORITHM

Abbreviations: AdV = adenovirus; BCV = brincidofovir; c/mL = copies per milliliter; UND = undetectable

APPENDIX 4. FLOW CHART FOR BRINCIDOFOVIR TOXICITY MANAGEMENT

Abbreviations: BCV = brincidofovir; QW = once weekly

APPENDIX 5. DEFINITIONS FOR PROBABLE OR DEFINITIVE ADENOVIRUS INFECTION OR DISEASE

Table 16: Definitions and Criteria for Probable or Definitive Adenovirus Disease

Probable	Definitive
Cardiac AdV Infection or Disease	

 • AdV detected by viral blood culture, or by a positive or detectable AdV DNA PCR value in blood or plasma • AND other causes (e.g., HIV, bacterial infection) ruled out • AND at least one of the following suggestive signs/symptoms: 
 – dyspnea – chest pain – peripheral edema • AND confirmation of heart enlargement or pericardial effusion by imaging 	
 • AdV detected on cardiac or pericardium biopsy via antigen/IHC, culture, or PCR • AND at least one of the following suggestive signs/symptoms: 
 – dyspnea – chest pain – peripheral edema • AND confirmation of heart enlargement or pericardial effusion by imaging
Gastrointestinal AdV Infection or Disease	

 • AdV isolated from intestinal biopsy by PCR 
OR • AdV detected by viral culture, or by AdV DNA PCR (positive or detectable value) in both stool and blood (with plasma \geq 1000 copies/mL) • AND other causative agents (e.g., bacterial, viral, amoebic) ruled out • AND endoscopic evidence of lesions (macroscopic or microscopic) not attributed to GVHD (i.e., biopsy-proven) • AND suggestive signs or symptoms (e.g., diarrhea, abdominal pain, ileus, vomiting, GI hemorrhage) 	
 • AdV detected on intestinal biopsy via antigen/IHC, culture or PCR • AND EITHER: 
 – Suggestive signs or symptoms (e.g., diarrhea, abdominal pain, ileus, vomiting, GI hemorrhage) and – Endoscopic evidence of lesions (macroscopic or microscopic) not attributed to GVHD 
OR • Cytopathic adenoviral aspect identified on biopsy

Table 16: Definitions and Criteria for Probable or Definitive Adenovirus Disease (Continued)

Probable	Definitive
Hepatic AdV Infection or Disease	

 • AdV detected by viral blood culture, or by a plasma AdV DNA PCR \geq 1000 copies/mL • AND other causative agents (e.g., hepatitis viruses) and causes (e.g., drug-induced, GVHD) ruled out • AND at least one of the following confirmed laboratory abnormalities: 
 – ALT > 5x ULN – AST > 5x ULN – serum total bilirubin > 5x ULN 	
 • AdV identified via hepatic biopsy via antigen/IHC or culture • AND at least one of the following confirmed laboratory abnormalities: 
 – ALT > 5x ULN – AST > 5x ULN – serum total bilirubin > 5x ULN
Central Nervous System AdV Infection or Disease	

 • AdV detected by viral blood culture, or by a positive or detectable AdV DNA PCR value in blood or plasma • AND other causes (e.g., bacterial, amoebic and stroke/infarct/CSF leak) ruled out • AND at least two of the following: 
 – Abnormal CSF – Focal deficit – Cognitive impairment – Visual symptoms – Seizure – Evidence of lesions by CT scan or MRI 	
 • AdV identified in CSF via antigen/IHC, culture or PCR • AND at least one of the following signs/symptoms of encephalitis: 
 – Abnormal CSF – Focal deficit – Cognitive impairment – Visual symptoms – Seizure – Evidence of lesions by CT scan or MRI

Table 16: Definitions and Criteria for Probable or Definitive Adenovirus Disease (Continued)

Probable	Definitive
Renal AdV Infection or Disease	

 • AdV detected by viral culture, or by AdV DNA PCR (positive or detectable value) in both urine and blood (with plasma \geq 1000 copies/mL) • AND other causes (e.g., bacterial, drug-induced) ruled out • AND at least one of the following: 
 – Suggestive signs or symptoms (impaired renal function, proteinuria, microscopic hematuria, dysuria) – Enlarged kidney on imaging – Renal/bladder obstruction 	
 • AdV identified via renal or bladder biopsy via antigen/IHC or culture • AND at least one of the following: 
 – Suggestive signs or symptoms (impaired renal function, proteinuria, microscopic hematuria, dysuria) – Enlarged kidney on imaging – Renal/bladder obstruction
Respiratory AdV Infection or Disease	

 • AdV identified in nasopharyngeal secretions, sputum, BAL, or endotracheal aspirate (culture, antigen or by PCR) • AND plasma AdV DNA PCR \geq 1000 copies/mL • AND no bacterial, fungal or other probable causative agent identified/cultured • AND both of the following: 
 – Suggestive signs or symptoms (cough, tachypnea, desaturation) – CT scan or x-ray with infiltrates 	
 • AdV identified in lung biopsy via PCR, culture, or via antigen/IHC methods • AND no bacterial, fungal or other probable causative agent identified/cultured • AND both of the following: 
 – Suggestive signs or symptoms (cough, tachypnea, desaturation) – CT scan or x-ray with infiltrates

Abbreviations: AdV = adenovirus; ALT = alanine aminotransferase; AST = aspartate aminotransferase; BAL = bronchoalveolar lavage; CSF = cerebrospinal fluid; CT = computed tomography; DNA = deoxyribonucleic acid; GI = gastrointestinal; GVHD = graft versus host disease; HIV = human immunodeficiency virus; IHC = immunohistochemistry; MRI = magnetic resonance imaging; PCR = polymerase chain reaction; ULN = upper limit of normal

APPENDIX 6. HCT COMORBIDITY INDEX SCALE

The following table, adapted from Sorror et al ([Sorror 2005](#)), should be used for assessing HCT comorbidities.

Table 17: Definitions of HCT Comorbidities

HCT Comorbidity	Definition	Score
Arrhythmia	Atrial fibrillation or flutter, sick sinus syndrome, or ventricular arrhythmia	1
Cardiac	Coronary artery disease ^a , congestive heart failure, myocardial infarction, or EF ≤ 50%	1
Inflammatory bowel disease	Crohn's disease or ulcerative colitis	1
Diabetes	Requiring treatment with insulin or oral hypoglycemic medication, but not diet alone	1
Cerebrovascular disease	Transient ischemic attack or cerebrovascular accident	1
Psychiatric disturbance	Depression or anxiety requiring psychiatric consult or treatment	1
Hepatic, mild	Chronic hepatitis, bilirubin > ULN to 1.5x ULN, ALT > ULN to 2.5x ULN, or AST > ULN to 2.5x ULN	1
Obesity	Body mass index ≥ 35 kg/m ²	1
Infection	Requiring continuation of antimicrobial treatment after Day 0 (Day 0 = day of transplant)	1
Rheumatologic	SLE, RA, polymyositis, mixed CTD, or polymyalgia rheumatica	2
Peptic ulcer	Requiring treatment	2
Renal, moderate to severe	Serum creatinine > 2 mg/dL (SI: 177 μmol/L), on dialysis, or prior renal transplantation	2
Pulmonary, moderate	DLco and/or FEV ₁ 66% to 80% or dyspnea on slight activity	2
Prior solid tumor	Treated at any time point in the patient's past history, excluding non-melanoma skin cancer	3
Heart valve disease	Except mitral valve prolapse	3
Pulmonary, severe	DLco and FEV ₁ ≤ 65% or dyspnea at rest or requiring oxygen	3
Hepatic, moderate or severe	Liver cirrhosis, bilirubin > 1.5x ULN, ALT > 2.5x ULN, or AST > 2.5x ULN	3

^a One or more vessel-coronary artery stenosis requiring medical treatment, stent or bypass graft.

Abbreviations: ALT = alanine aminotransferase; AST = aspartate aminotransferase; CTD = connective tissue disorder; DLco = diffusion capacity of carbon monoxide; EF = ejection fraction; FEV₁ = forced expiratory volume in the first second; RA = rheumatoid arthritis; SLE = systemic lupus erythematosus; ULN = upper limit of normal reference range.

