5.3.4. Exploratory Endpoints

- Association of HCT co-morbidity index and clinical outcomes

- Change from baseline in exploratory biomarker laboratory parameters (e.g., citrulline, ST2, TIM3, and CRP)
- Association of exploratory biomarkers with treatment-emergent CTCAE Grade 2 diarrhea or GI GVHD
- Number of and reasons for emergency room (A&E) visits; number of, duration, and reasons for hospital admissions; number of days spent in ICU, in isolation, or confined to bed; other infections; receipt of and duration of relevant concomitant medications and therapies; type and number of certain diagnostic or therapeutic procedures; and provision of home healthcare through Week 16
- Association between immune reconstitution and viral response and clinical outcome (e.g., based on measurement and activity of AdV-specific cytotoxic T lymphocytes [CTLs] and other immune reconstitution parameters)

[figure not shown]

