7.2. Subject Exclusion Criteria

Subjects who meet *any* of the following criteria, as applicable, are not eligible to participate in this study. Retesting of exclusionary laboratory results (through the designated central laboratory) is permitted.

[Note: The CTCAE grading scales for diarrhea ([Table 7](#)) and the NIH staging scales for acute GVHD ([Appendix 1](#)) will be used to determine eligibility into this study. Current stool output or volume, as appropriate, should be compared with each subject's pre-transplant stool output or volume (= baseline). Contact the Chimerix Medical Monitor (or designee) for eligibility questions where baseline stool output or volume is unknown or the subject's clinical condition warrants consideration of an alternative baseline measure.]

1. Any CTCAE Grade 4 diarrhea (i.e., life-threatening consequences with urgent intervention indicated) within 7 days prior to Day 1
2. Any CTCAE Grade 2 or 3 diarrhea (i.e., increase of ≥ 4 stools per day over baseline), unless attributed to AdV, within 7 days prior to Day 1
3. NIH Stage 4 acute GVHD of the skin (i.e., generalized erythroderma with bullous formation) within 7 days prior to Day 1
4. NIH Stage 2 or higher acute GVHD of the liver (i.e., bilirubin > 3 mg/dL [SI: > 51 $\mu\text{mol/L}$]) within 7 days prior to Day 1
5. NIH Stage 2 or higher acute GVHD of the gut (i.e., diarrhea > 556 mL/m²/day, or severe abdominal pain with or without ileus) within 7 days prior to Day 1

6. Active malignancy (with the exception of non-melanoma skin cancer), including relapse or progression of the underlying disease for which qualifying transplant was performed
7. Use of vasopressors within 7 days prior to Day 1
8. PT-INR > 2x upper limit of normal reference range (ULN) in the absence of anticoagulation within 7 days prior to Day 1
9. Requirement for mechanical ventilation within 7 days prior to Day 1, or sustained oxygen delivery for > 24 hours within 7 days prior to Day 1, or any oxygen requirement within 48 hours prior to Day 1
10. Estimated creatinine clearance < 30 mL/min or use of renal replacement therapy (e.g., hemodialysis, continuous renal replacement therapy, peritoneal dialysis) within 7 days prior to Day 1
11. ALT > 5x ULN, AST > 5x ULN, or total bilirubin > 3 mg/dL [SI: > 51 µmol/L] within 7 days prior to Day 1

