11.4. HCT Comorbidities Assessment

HCT comorbidities present at baseline will be scored using the HCT comorbidity index assessment (Sorrer 2005) (see Appendix 6 for scoring table).

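### Table 17 (Appendix 6): the two pulmonary rows are inconsistent, so a symptom-free child with one lung-function value ≤ 65% and the other > 80% scores 0, while a milder single value scores 2

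*Combined protocol and SAP*

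**What the plan says.** Section 11.4 states that "HCT comorbidities present at baseline will be scored using the HCT comorbidity index assessment" and refers to Appendix 6 for the scoring table. Appendix 6 says that its Table 17, adapted from a cited publication, "should be used for assessing HCT comorbidities".

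Two rows of that table grade lung disease:

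- Moderate, 2 points: the lung-function limb opens "DLco and/or FEV" (FEV1 in the table) and continues "66% to 80% or dyspnea on slight activity".
- Severe, 3 points: DLco *and* FEV1, followed by "≤ 65% or dyspnea at rest or requiring oxygen".

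The only table footnote that explains a score concerns coronary artery disease. Nothing in Appendix 6 or Section 11.4 says how to score one value ≤ 65% when the other is higher.

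The index serves one exploratory objective (Section 5.2.2) and one exploratory endpoint, "Association of HCT co-morbidity index and clinical outcomes" (Section 5.3.4).

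**The concern.** Two grades of the same organ should fit together: once a child leaves the moderate range by getting worse, the severe row should take over. Here the moderate row needs only one measure in its range but has a floor of 66%, and the lung-function limb of the severe row needs both measures at or below 65%. An isolated low value drops out of the first row without entering the second.

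At stake is the ordering of one item of the index. Some children with a marked single deficit would be grouped with unaffected children, or with moderately affected ones, when the index is related to outcome. A second risk is uneven scoring: a rater who reads the severe row loosely, as either measure, gives 3 points where a literal rater gives 0 or 2.

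**Working it through.** The plan states no figure on this point, so there is none to reproduce. The check applies the two rows literally.

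**Inputs (Table 17).** For a child with no listed dyspnea and no oxygen need:

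- 3 points if DLco ≤ 65% and FEV1 ≤ 65%
- otherwise 2 points if DLco or FEV1 lies in 66% to 80%
- otherwise 0

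**Scores for chosen pairs**

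| DLco / FEV1 (%) | As written | With and/or in the severe row |
|---|---|---|
| 90 / 90 | 0 | 0 |
| 73 / 90 | 2 | 2 |
| 60 / 90 | 0 | 3 |
| 73 / 73 | 2 | 2 |
| 60 / 73 | 2 | 3 |
| 60 / 60 | 3 | 3 |

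With FEV1 held at 90 and DLco falling 90 → 73 → 60, the score goes 0 → 2 → 0, which is a reversal. With FEV1 held at 73, the score is 2 throughout: flat, but not reversed.

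**All integer pairs from 30% to 110%.** A pair is reversed if raising one value, with the other unchanged, gives a higher score.

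- Reversed pairs have one value in 30 to 65 (36 values) and the other in 81 to 110 (30 values), in either order: 36 × 30 × 2 = 2,160. No other pair is reversed.
- Each has 15 better pairs (low value raised to 66 through 80) that score 2 against its 0: 2,160 × 15 = 32,400 reversed comparisons.
- With and/or in the severe row, the count is 0.

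These are counts of grid points, not of children. They show where the fault lies, not how often it would occur.

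**Symptoms.** At 60 / 90, dyspnea on slight activity gives 2 points, and dyspnea at rest or an oxygen need gives 3. The oxygen route is largely closed at baseline, because exclusion criterion 9 (Section 7.2) bars "any oxygen requirement within 48 hours prior to Day 1" and also sustained oxygen for more than 24 hours in the prior 7 days. Dyspnea at rest is not excluded.

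**Number of children.** Table 5 schedules no spirometry or DLco. Neither the safety procedures listed at the start of Section 11 nor the history items in Section 11.1 include one. Inclusion criterion 1 admits children from 2 months of age. How many children will have even one of the two values on record cannot be derived from the documents. Where only one value exists and it is ≤ 65%, the severe lung-function limb cannot be shown to be met.

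**The case against.** The strongest reply is that little depends on this. The index is not a stratification factor (Section 8.8) or a term in the primary ANCOVA, and the mortality non-inferiority analysis adjusts for advanced baseline disease instead (Section 12.4.1). It is not among the named subgroups (Section 12.9), although that list is left open. All of this stands, and it is why the point is minor.

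A second reply is that the table is adapted from a source not available here, so the plain *and* could be a slip, a deliberate change or the source's own wording. That also stands, and it is a reason to check the source before editing. It does not rescue the rule, because the fault lies in how the two rows combine, whatever their origin. Within Table 17, the other organ with two grades, hepatic, uses *or* in both rows, so one abnormal value is enough for the higher grade.

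Three stronger readings are tempting, and the documents do not support them:

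- A reader might infer that the whole index runs backwards. Only the pulmonary item reverses, and the total only through it.
- A reader might infer that 3 points require both values to be low. That is true of the lung-function limb alone, since dyspnea at rest also gives 3.
- A reader might infer that every isolated low value lowers the score. With the other value at 66% to 80%, the score merely fails to rise.

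**Conclusion.** Table 17 is wrong as written, at the lowest level of importance. On a literal reading, a symptom-free child with one value ≤ 65% loses 3 points on the pulmonary item if the other value is > 80% (0 instead of 3), or 1 point if the other value is 66% to 80% (2 instead of 3). The comparison score of 3 assumes that the severe row is meant to work like the moderate one, with either measure sufficient.

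The number affected is unknown and may be zero. Applying an assumed percentage to the planned 141 subjects would give a count that the documents do not support. Nor do they allow the effect on the association between index and outcome to be calculated, since no model for that analysis is given. No primary, key secondary or safety conclusion depends on it.

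**What to change.** In Table 17, reconcile the two pulmonary rows after checking them against the cited source of the index. Use and/or in the lung-function limb of the severe row, so that a single value ≤ 65% scores 3, and add a footnote that the worse of the two values sets the grade.

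The cost is a small wording edit in Appendix 6. It needs no new test, visit or data item. It is best made before baseline scoring begins, so that all sites score alike.
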